Statistical analysis: Demographic and clinical data was analyzed at baseline to measure the balance among the study groups. Quantitative variables were described using mean \pm standard deviation or median and 25th-75th percentiles (Q1, Q3) depending on their distribution. Qualitative variables were described using frequency and percentage distributions. Next, we showed that our variables distribute equally between the study groups. For comparing normally distributed variables between our study groups, we used the ANOVA test. For comparing variables that do not distribute normally between our study groups, we used the Kruskal-Wallis test with adaptation to pairwise comparison. For comparing qualitative variables between our study groups, we used the independent Chi-square test and Fisher exact test. Bonferroni adjustment was used for multiple comparisons for each independent comparison of true acupuncture vs sham-control, true acupuncture vs SOC-control and sham-control vs SOC-control. Since the variation of dyspnea intensity between day 1 and day 2 had a normal distribution, a multivariate linear regression analysis was performed after collinearity, interaction and confounding analysis, in order to neutralize the effect of the different sociodemographic and medical covariates on the primary outcome in the 3 study arms. The adjusted unstandardized regression coefficients were given with confidence interval (CI), while

a $p < 0.05$ was considered as statistically significant. Data analysis was performed using IBM SPSS version 22 statistics software.

Results:

Baseline patient data: 104 patients were screened for eligibility from November 2017 to February 2020. Among them, 72 met inclusion criteria and were recruited. Twenty-six of them were assigned to the true acupuncture arm, 24 to the sham-control arm, and 22 to the SOC-control arm. Baseline demographic and clinical characteristics were similar in patients from the 3 study arms as shown in Table 1. To note, all the patients randomized to any of the three groups completed treatments per-protocol (Fig. 1).

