- *Treatment failure:*

No death or mechanical ventilation occurred in the study participants during follow-up. However there had a total of 4 treatment failures, all of them were non-invasive ventilations, which occurred in 2 (8%) patients in the true acupuncture arm, 1 (4.3%) in the sham-control arm and 1 (5%) in the SOC-control arm ($p=0.83$).

- *Duration of hospitalization:*

No difference was noted in terms of duration of hospitalization between the three study arms (5.5 ± 2.3 days for true acupuncture vs. 6.0 ± 2.9 days for sham-control and 6.3 ± 2.9 days for SOC-control, $p=0.050$).

- *Safety:*

No side effect of acupuncture treatment was reported during the study period as assessed by the Acup-AE questionnaire.

Tables and Figures:

Table 1: Baseline characteristics

[figure not shown]
Characteristics	True acupuncture (N=26)	Sham-control (N=24)	SOC-control (N=22)	p
Age (mean ± SD)	69.2±10.1	70.7±8.1	67.4±9.3	0.47
Gender (Men)	20 (77%)	15 (62%)	17 (77%)	0.43
Comorbidities				
Cardiovascular	18 (69%)	20 (83%)	15 (68%)	0.42
Respiratory (other than COPD)	7 (27%)	2 (8%)	5 (23%)	0.23
Gastroenterological	2 (8%)	4 (17%)	5 (23%)	0.34
Renal / Urologic	7 (27%)	3 (12%)	5 (23%)	0.44
Metabolic / Endocrinological	15 (58%)	13 (54%)	13 (59%)	0.94
Hematological / Oncological	3 (12%)	6 (25%)	3 (14%)	0.40
Neurological	4 (15%)	0 (0%)	1 (5%)	0.09
Smoking status				
Smoker	13 (50%)	16 (67%)	14 (64%)	0.44
Former smoker	13 (50%)	8 (33%)	8 (36%)	
Never smoked	0	0	0	
CCI (median [Q1, Q3])	6.0 [3.5, 6.0]	5.0 [4.0, 6.75]	4.5 [3.0, 7.25]	0.87
COPD severity				
Mild: FEV1 ≥ 80%	1 (4%)	0 (0%)	1 (5%)	
Moderate: 50% ≤ FEV1 < 80%	4 (15%)	5 (21%)	5 (23%)	0.69
Severe: 30% ≤ FEV1 < 50%	7 (27%)	11 (46%)	9 (41%)	
Very severe: FEV1 < 30%	5 (19%)	4 (17%)	4 (18%)	
Unknown	9 (35%)	4 (17%)	3 (14%)	
Pulmonary hypertension				
None	10 (38%)	15 (62%)	16 (73%)	
Mild: mPAP = 25-40 mmHg	4 (15%)	3 (12%)	3 (14%)	
Moderate: mPAP = 41-55 mmHg	3 (12%)	0	2 (9%)	0.11
Severe: mPAP > 55 mmHg	0	0	0	
Unknown	9 (35%)	6 (25%)	1 (5%)	
COPD exacerbation hospitalizations				
0	19 (73%)	12 (50%)	9 (41%)	
1-4	6 (23%)	11 (46%)	9 (41%)	0.09
≥5	1 (4%)	1 (4%)	4 (18%)	
Treatment				
Inhalations	24 (92%)	23 (96%)	22 (100%)	0.41
Systemic corticosteroids	3 (12%)	3 (13%)	1 (5%)	0.61
Theophylline	0	0	1 (5%)	0.32
Oxygen home therapy	8 (31%)	12 (52%)	8 (36%)	0.29
BiPAP	4 (15%)	2 (8%)	4 (18%)	0.60
APACHE-II at admission (mean ± SD)	13.3±3.6	12.0±4.4	11.0±3.8	0.14
Baseline data (median [Q1, Q3])				

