Dyspnea (mBorg)	8.0 [5.5, 8.75]	6.5 [5.0, 8.5]	7.75 [6.0, 8.5]	0.82
Cough (VAS)	7.5 [5.0, 8.0]	5.0 [5.0, 7.4]	5.0 [3.6, 7.5]	0.35
Sputum (VAS)	6.0 [1.5, 7.5]	6.0 [4.25, 6.0]	5.0 [1.9, 6.0]	0.22
O₂ saturation				
≤ 80%	4 (15%)	1 (4%)	0	0.30
81-89%	9 (35%)	10 (42%)	10 (45%)	
≥ 90%	13 (50%)	13 (54%)	12 (55%)	
PCO₂ (mmHg)				
< 45	6 (23%)	3 (12%)	8 (36%)	
45-60	12 (46%)	17 (71%)	9 (41%)	0.10
60-80	5 (19%)	4 (17%)	5 (23%)	
> 80	3 (12%)	0	0	
pH				
< 7.2	0	0	0	
7.2-7.3	5 (19%)	4 (17%)	1 (5%)	0.30
> 7.3	21 (81%)	20 (83%)	21 (95%)	
Respiratory rate (/min) (median [Q1, Q3])	21 [16, 23.75]	22 [16.5, 26]	20 [16, 22]	0.26

Legend: CCI: Charlson Comorbidity Index; mPAP: Mean Pulmonary Arterial Pressure; SOC: Standard-Of-Care.

Table 2: Multivariate linear regression analysis on variation of dyspnea from day 1 to day 2

Factors and covariates	Adjusted unstandardized coefficient (B)	95% Confidence interval		p value
		Inferior	Superior	
Constant (Intercept)	2.088	-3.409	7.584	0.457
Study Arm				
True acupuncture	2.172	0.421	3.923	0.015
Sham-control	0.390	-1.319	2.099	0.655
SOC-control	0	-	-	-
Cardiovascular comorbidities (0=No, 1=Yes)	-0.322	-2.935	1.391	0.713
Gastroenterological comorbidities (0=No, 1=Yes)	4.703	2.527	6.879	<0.001
Hospitalizations for COPD in the last year	-0.379	-0.756	-0.003	0.048
Age	-0.040	-0.133	0.053	0.400
APACHE-II	0.118	-0.099	0.336	0.287
Charlson Comorbidity Index	-0.026	-0.406	0.354	0.894

Figure 1: Flow-chart

Legend: SOC: Standard-of-care.

Figure 2: Between-group comparison of patient-reported outcomes

[figure not shown]

Figure 3: Between-group comparison of physiologic features

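### Non-significant three-group baseline tests are presented as showing equal arms; Table 1 has gaps on predictors in the trial's own model, pulling in opposite directions, and the per-day dyspnea tests are unadjusted

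*Combined protocol and SAP*

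**What the plan says.** The Statistical analysis section describes baseline testing and then states: "Next, we showed that our variables distribute equally between the study groups". The tests are named there: "For comparing normally distributed variables between our study groups, we used the ANOVA test", Kruskal-Wallis for non-normal variables, and "For comparing qualitative variables between our study groups, we used the independent Chi-square test and Fisher exact test". A p-value below 0.05 "was considered as statistically significant".

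Under Results, Baseline patient data, the arm sizes are given ("Twenty-six of them were assigned to the true acupuncture arm, 24 to the sham-control arm, and 22 to the SOC-control arm"), and the conclusion is "Baseline demographic and clinical characteristics were similar in patients from the 3 study arms as shown in Table 1". Table 1 gives one three-group p-value per variable; the smallest is 0.09. It gives no standardised differences, no pairwise baseline contrasts and no margin for calling arms equivalent.

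Table 1 lists "COPD exacerbation hospitalizations" in three classes (0, 1-4, 5 or more). Table 2, the regression on the change in dyspnea from day 1 to day 2, includes "Hospitalizations for COPD in the last year" together with APACHE-II, gastroenterological and cardiovascular comorbidity, age and the Charlson index. It has no baseline dyspnea term. The day-by-day dyspnea comparisons under Results, Primary outcome are reported without covariates.

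**The concern.** A p-value above 0.05 means that a difference was not detected. It shows equality only if the test would very probably have detected any gap that matters, and arms of 22 to 26 patients do not allow that. A three-group test also spreads its power over all contrasts, so a sizeable gap between two arms can sit behind an unremarkable overall p-value.

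The primary outcome is dyspnea before and after treatment over four days, yet adjustment is reported only for the day 1 to day 2 change. A reader told that the arms are equal has no reason to ask whether prognostic differences affect the unadjusted day 1 to day 3 comparisons. If the differences are on variables that the trial's own model finds predictive, that question is open.

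**Working it through.** **Inputs.** Arm sizes 26 / 24 / 22 (acupuncture / sham / SOC-control). From Table 1: APACHE-II 13.3±3.6, 12.0±4.4, 11.0±3.8; prior COPD hospitalizations none 19/12/9, 1-4 6/11/9, 5 or more 1/1/4; gastroenterological comorbidity 2/4/5. From Table 2: hospitalizations B = -0.379 (95% CI -0.756 to -0.003, p=0.048), gastroenterological comorbidity B = 4.703 (2.527 to 6.879, p<0.001), APACHE-II B = 0.118 (p=0.287), acupuncture vs SOC-control B = 2.172 (p=0.015).

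**1. The printed p-values reproduce.**
- APACHE-II: grand mean (26×13.3 + 24×12.0 + 22×11.0)/72 = 12.16. Between-group mean square 64.0/2 = 32.0. Within-group mean square (25×3.6² + 23×4.4² + 21×3.8²)/69 = 15.54. F = 2.06 on 2 and 69 df, p = 0.135 (printed 0.14).
- Hospitalizations: Pearson chi-square on the 3×3 table = 8.10, 4 df, p = 0.088 (printed 0.09).

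So Table 1 is not miscalculated on these rows. What fails is the inference from it.

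**2. What such a test can detect.** Noncentrality is Σ nᵢ(μᵢ − μ̄)²/σ². For a 0.5 SD gap with sham midway, μ̄ = (26×0.5 + 24×0.25)/72 = 0.264, the noncentrality is 2.99 and the power about 31%. For 0.6 SD it is 2.99 × (0.6/0.5)² = 4.30, and the power about 43%. For the APACHE-II means as reported, power is about 41%.

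**3. Acupuncture vs SOC-control.** The standardised difference is the difference divided by √((s₁² + s₂²)/2), with s² = p(1−p) for proportions.
- APACHE-II: 2.3/√((3.6² + 3.8²)/2) = 2.3/3.70 = 0.62. The difference of 2.3 points has 95% CI 0.15 to 4.45.
- Any prior hospitalization: 7/26 = 26.9% vs 13/22 = 59.1%, difference -32 points (95% CI -59 to -5), standardised -0.69.
- Gastroenterological comorbidity: 2/26 = 7.7% vs 5/22 = 22.7%, standardised -0.43.

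For acupuncture vs sham, APACHE-II differs by 0.32 SD and any prior hospitalization (27% vs 50%) by 0.49 SD.

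**4. What the gaps could be worth in mBorg units.** A positive coefficient is read as more improvement, which matches how the results describe the acupuncture effect. Let x be the mean of the 1-4 class and y the mean of the top class. Neither is given, so x = 1.5 to 2.5 and y = 5 to 7 are assumed.
- Mean hospitalizations: acupuncture (6x + y)/26, SOC-control (9x + 4y)/22. Low case: 0.54 vs 1.52, gap 0.98. High case: 0.85 vs 2.30, gap 1.45. Multiplied by 0.379: **+0.37 to +0.55**, towards acupuncture. Wider assumptions (x 1 to 4, y 5 to 8) give +0.34 to +0.70. Over the limits of the slope's own CI the shift runs from 0.98×0.003 ≈ 0 to 1.45×0.756 ≈ 1.1.
- Gastroenterological comorbidity: 4.703 × (2/26 − 5/22) = 4.703 × (−0.150) = **-0.71**, against acupuncture.
- APACHE-II: 0.118 × 2.3 = +0.27, from a non-significant coefficient.

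The first two together: -0.33 to -0.16. With APACHE-II: -0.06 to +0.11, close to zero.

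**5. The 'Unknown' rows.** The printed p-values for COPD severity (0.69) and pulmonary hypertension (0.11) reproduce with 'Unknown' counted as a category (0.694 and 0.112). Without it they are 0.926 and 0.368. These two rows therefore test disease category and missing data together. Pulmonary hypertension is unknown in 9/26 (35%) of the acupuncture arm and 1/22 (5%) of SOC-control.

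**The case against.** The strongest reply is that randomization, not observed equality in Table 1, justifies the unadjusted tests. Table 1 has more than 20 variables and three pairs of arms, so some gaps of this size are expected by chance. Pairwise p-values for acupuncture vs SOC-control (APACHE-II 0.037; none vs any hospitalization 0.039, Fisher) become 0.11 and 0.12 after the trial's own Bonferroni factor of three. The regression already contains all three variables, and acupuncture remains significant there. All of this stands, and nothing here suggests faulty randomization.

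It does not rescue the equality sentence, which claims a demonstration that the tests cannot give. Nor does it extend the adjustment beyond the day 1 to day 2 change. How much an imbalance matters depends on its size and prognostic weight, not on its p-value.

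Three stronger readings are tempting, and the documents do not support them:
- *The imbalance favours acupuncture throughout.* This follows only if hospitalizations are taken alone. Gastroenterological comorbidity, which has the smallest p-value in Table 2, pulls the other way and by more. The slopes also describe the day 1 to day 2 change, not score levels on days 1 to 3.
- *Some 17 to 25% of the reported 2.17 (0.37/2.17 to 0.55/2.17) is confounding.* The 2.17 is already adjusted for hospitalizations, APACHE-II and gastroenterological comorbidity.
- *Counting 'Unknown' hid severity gaps.* Leaving it out raises both p-values, so the known categories look more alike. The fault is that missing data are mixed into a severity test.

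**Conclusion.** The point holds as a false claim of equality combined with adjustment of limited reach. It is not a finding of bias. For acupuncture vs SOC-control the standardised gaps are 0.62 (APACHE-II), 0.69 (any prior hospitalization) and 0.43 (gastroenterological comorbidity), and the last two variables are significant predictors in Table 2. Their implied shifts have opposite signs, so the net direction for the unadjusted per-day dyspnea comparisons cannot be determined from the documents. The day 1 to day 2 regression result is not called into question here.

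This rests on three assumptions: the hospitalization rows of Tables 1 and 2 are the same variable (Table 1 gives no time window); the class means are as assumed; and, for the mBorg figures only, the day 1 to day 2 slopes carry over to other comparisons.

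**What to change.** - Delete the equality sentence, and replace the statement that the arms were similar with a description of the differences seen.
- Drop the baseline p-values from Table 1. Report standardised differences for each pair of arms, and show 'Unknown' as missing data outside the severity categories.
- Extend covariate adjustment from the day 1 to day 2 change to the other dyspnea comparisons, by a proportional-odds model or rank ANCOVA. Use one covariate set for all of them, chosen on prognostic grounds and not because a variable is imbalanced: baseline dyspnea plus the covariates already in Table 2, including prior hospitalizations, APACHE-II and gastroenterological comorbidity.
- Because the document already reports results, label the extended analyses as added afterwards and show them beside the unadjusted ones.

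The cost is rewording, a revised Table 1 and a re-run with data already collected. The per-day results may shift slightly in either direction.

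### The document names chi-square and Fisher's exact test without a rule for choosing; its sparse-table p-values look like Pearson chi-square throughout, and for treatment failure the exact p is 1.00, not 0.83.

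*Combined protocol and SAP*

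**What the plan says.** The Statistical analysis section covers categorical data in one sentence: "For comparing qualitative variables between our study groups, we used the independent Chi-square test and Fisher exact test". It does not say when each test applies. The significance level is 0.05.

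Under Outcomes, treatment failure is a secondary outcome that combines in-hospital death with a need for noninvasive or mechanical ventilation. The Results count four failures, each of them a case of noninvasive ventilation. The breakdown by arm reads: "which occurred in 2 (8%) patients in the true acupuncture arm, 1 (4.3%) in the sham-control arm and 1 (5%) in the SOC-control arm". The printed p-value is 0.83, and no test is named.

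On denominators, Baseline patient data gives: "Twenty-six of them were assigned to the true acupuncture arm, 24 to the sham-control arm, and 22 to the SOC-control arm". It adds that "all the patients randomized to any of the three groups completed treatments per-protocol".

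Table 1 prints a p-value for each of 20 categorical characteristics, again without naming the test. One sparse example is "Inhalations 24 (92%) 23 (96%) 22 (100%) 0.41".

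**The concern.** Four events over three arms are too few for the chi-square approximation, and an exact test was already among the named methods. A reader of the Statistical analysis section would expect Fisher's test to have been used where counts are this small. The printed value is one that Fisher's test cannot give for the printed counts.

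Two things are at stake. First, the p-value of a reported secondary outcome, and those of many baseline rows, rest on an approximation that is unreliable at these counts. Second, a p-value of 0.83 with no comment on the event count may be taken as evidence that the arms are alike, when the comparison had almost no capacity to show a difference.

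**Working it through.** **Inputs.** Failures 2/1/1 (Results, Treatment failure); arms 26/24/22, total 72 (Baseline patient data); cell counts from Table 1. A second set of arms, 25/23/22, is an assumption. It is compatible with the printed percentages: 2/25 = 8.0%, 1/23 = 4.3%, 1/22 = 4.5%, printed as 5%.

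**1. Reproducing 0.83.** With overall failure proportion q, expected failures are E = n × q. Then X² = Σ(O − E)²/E ÷ (1 − q), and on 2 df p = exp(−X²/2).

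- 26/24/22: q = 4/72; E = 1.44, 1.33, 1.22. Σ(O − E)²/E = 0.214 + 0.083 + 0.040 = 0.337. X² = 0.337/0.944 = 0.357; p = 0.836, which is 0.84 rounded or 0.83 truncated.
- 25/23/22: q = 4/70; E = 1.43, 1.31, 1.26. Σ(O − E)²/E = 0.229 + 0.075 + 0.053 = 0.356. X² = 0.356/0.943 = 0.378; p = 0.828, which rounds to 0.83.

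In both sets three of the six cells have expected counts far below 5.

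**2. Exact test.** Given 4 failures, the probability of a split a/b/c is C(26,a)·C(24,b)·C(22,c)/C(72,4), with C(72,4) = 1,028,790. For 2/1/1 this is 325 × 24 × 22/1,028,790 = 0.167. The next most probable split, 1/2/1, has 0.153. The observed split is therefore the most probable one, every split counts as at least as extreme, and p = 1.00. The same holds on 25/23/22 and on every other set tried (24–26/23–24/19–22).

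**3. What 4 events can show (26/24/22).** The three least probable splits have all failures in one arm: C(22,4) = 7,315, C(24,4) = 10,626 and C(26,4) = 14,950. Their cumulative sums over 1,028,790 give exact p = 0.007 (all SOC-control), 0.017 (all sham-control) and 0.032 (all true acupuncture). The next split, 0/1/3, adds 24 × 1,540 = 36,960 and gives 69,851/1,028,790 = 0.068. So only an all-in-one-arm split reaches p<0.05.

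**4. Table 1.** Fifteen of the 20 categorical rows have an expected count below 5. All 15 printed values equal Pearson to two decimals, and none equals the exact value. Examples:

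| Row | Printed | Pearson | Exact |
|---|---|---|---|
| Inhalations | 0.41 | 0.414 | 0.770 |
| O₂ saturation | 0.30 | 0.299 | 0.407 |
| PCO₂ | 0.10 | 0.102 | 0.153 |
| Pulmonary hypertension | 0.11 | 0.112 | 0.066 |
| Systemic corticosteroids | 0.61 | 0.613 | 0.690 |

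COPD severity and pulmonary hypertension match with Unknown kept as a category. Home oxygen is not sparse; it matches Pearson only with 23 sham patients (0.29, against 0.36 with 24), which its printed 52% = 12/23 also implies.

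**The case against.** The strongest objection is that nothing was breached. The sentence names chi-square as well as Fisher's test and reserves neither for sparse tables. This stands. A reader might infer that the document prescribes Fisher's test for small counts and that the analysis departed from it; the text does not say so. What remains is a missing rule and an unsuitable choice between two named tests.

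Second, Pearson is inferred from values. On the randomized arms it rounds to 0.84, and the 25/23/22 arms appear nowhere in the document. Arms of 26/23/22 also fit the printed percentages but give 0.849. On 25/23/22 the likelihood-ratio test also rounds to 0.83 (0.834). Even the exact test would give 0.83 for a 1/2/1 split on 26/24/22 (1 − 0.167 = 0.833), although the printed counts and percentages are 2/1/1. For this one value the attribution is therefore only probable; the Table 1 pattern is what makes it likely.

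Third, that pattern has loose ends. Corticosteroids prints 3 sham patients as 13%, while 3 of 24 is printed as 12% in other rows, which hints at 23 patients; yet 0.61 matches only with 24 (with 23, Pearson is 0.593). Some non-sparse rows do not separate the tests: for cardiovascular comorbidity both give 0.42.

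Fourth, the effect is slight. The counts are openly printed, and the Table 1 rows are baseline comparisons in a randomized trial. This also stands. Nor can treatment failure be called the trial's only hard outcome, since duration of hospitalization and blood gases are secondary outcomes too.

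**Conclusion.** The point holds and is minor. For the printed 2/1/1 split, 0.83 cannot be the exact p-value. The exact value is 1.00 whichever plausible denominators are used. The sparse p-values in Table 1 appear to be Pearson chi-square without exception, although Fisher's test is stated to have been used. The changes go in both directions: most of the examples rise, while pulmonary hypertension falls from 0.11 to 0.07.

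No result crosses 0.05, so the finding of no detected difference in treatment failure is unchanged. A reader might go further and conclude that the arms are similar on this outcome; four events cannot support that under either test. A reader might also take the 4.3% as proof that a sham patient was lost. It implies 1/23 rather than 1/24 (4.2%) and conflicts with 24 patients completing, but the document does not say which denominator was used.

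The conclusion rests on the printed counts being correct, on Unknown being a category in the two rows noted, and on 24 sham patients in the corticosteroids row.

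**What to change.** - Replace the sentence on qualitative variables with a rule: Fisher's exact test (Fisher-Freeman-Halton for three arms) whenever an expected count is below 5, otherwise Pearson chi-square. The threshold of 5 is a convention; what matters is that a rule is stated.
- Report treatment failure with exact p=1.00 in place of 0.83, give the denominator for each arm, and reconcile 4.3% with 24 sham patients.
- Add one sentence: with 4 failures only a split with all 4 in one arm could have reached p<0.05, so the result is not evidence of similarity.
- Re-run the 15 sparse Table 1 rows with the exact test, and state the sham denominator for home oxygen and systemic corticosteroids.

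The cost is two sentences and a re-run of a few cross-tables with a test the document already names. No new data and no design change are needed.

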Official title: Treatment of acute exacerbations of chronic obstructive pulmonary disease with acupuncture during hospitalization: a three-arm double-blinded randomized sham-controlled trial

NCT number: NCT03398213

Date of the document: June 3, 2020

Methods:

Study design: This is a three-arm 1:1:1 randomized-controlled trial evaluating the efficacy and safety of the addition of acupuncture to SOC as compared to sham-procedure added to SOC (sham-control) and to SOC only (SOC-control) for treatment of AECOPD in patients hospitalized in internal medicine departments. The study protocol was reviewed and approved by the Institutional Review Board (IRB) in accordance with the Helsinki Declaration (0108-17-BNZ) and registered at www.clinicaltrials.gov (NCT03398213). Trial methods and results were reported according to the Consolidated Standards of Reporting Trials (CONSORT) 2010 guidelines.¹⁹

Participants: Patients hospitalized in internal medicine departments with a previous diagnosis of COPD³ were evaluated by department physicians. Inclusion criteria included a previous diagnosis of COPD and a clinical diagnosis of AECOPD as defined by the GOLD criteria.³ Exclusion criteria included hemodynamic instability, a platelet count below $20 \times 10^9/L$, expected respiratory deterioration requiring mechanical ventilation in the next 24 hours, or an inability to provide informed consent. Primary socio-demographic and medical data were recorded and compared between the three study groups.

Setting: The study was set in internal medicine departments of Bnai Zion medical center, a tertiary hospital in Haifa, Israel.

Interventions: The intervention protocol was based on a literature review and the Delphi process. A panel of eight acupuncturists of at least 5 years of experience in treating hospitalized patients were consulted. The experts were asked to review and analyze the literature regarding Traditional Chinese Medicine (TCM) and COPD, delineate relevant TCM syndromes and associated "critical" acupoints and treatment frequency. Their suggestions were based on literature data and their professional experience. Finally, three cycles of stepwise anonymous discussions were taken to obtain a consensus on the treatment approach. The conclusion was to

assign the patients into three groups for four daily consecutive treatment sessions and a 4-day follow-up.

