they were taught they are actually treating patients by stimulating ear acupoints and that the aim of the study was to compare the efficacy and safety of acupuncture administered by an experienced acupuncturist as compared to acupressure administered by unexperienced medical staff after a short training. Patients were told they are receiving ear-point stimulation. Therefore, this study arm was double blinded. SOC was administered as well as described earlier.

Outcomes:

The primary outcome was dyspnea intensity pre- and post-treatment in the 4 days of follow-up. It was measured daily, before and one hour after treatment (for acupuncture and sham-control groups) or after first evaluation (for SOC-control group), via the modified Borg (mBorg) scale, which is a validated scale that has been used to evaluate the degree of dyspnea (0- no dyspnea, to 10- worse dyspnea) in both stable COPD and AECOPD.^{21,22} Dyspnea intensity was chosen as primary outcome since it has been shown to predict clinical outcomes in AECOPD.²³

Secondary outcomes included:

Variation of clinical symptoms: Including cough intensity and sputum production associated with the AECOPD, as evaluated on a Visual Assessment Scale from 0 (no symptom) to 10 (maximally symptomatic), throughout the 4 days of evaluation.

Variation of physiologic features: Venous blood gases (pH and pCO₂) and oxygen saturation were measured before intervention and daily in the four evaluation days. Respiratory rate (RR) was measured daily, before and one hour after treatment (for true acupuncture and sham-control groups) or after first evaluation (for SOC-control group).

Treatment failure: Defined as death during hospitalization or need for noninvasive or mechanical ventilation. Treatment failure incidence was evaluated and compared between the three groups.

Duration of hospitalization: Evaluated and compared between the three study arms.

Safety: Acupuncture-related side effects were systematically evaluated after treatment in the true acupuncture group via the validated Acup-AE questionnaire administered to the patient by the acupuncturist immediately after therapy.²⁴

Minimal sample size: In a previous study evaluating the efficacy of acupuncture vs sham-acupuncture in 68 patients with chronic COPD (34 patients in each group), a 3.6±1.9 units improvement in dyspnea (according to mBorg scale) was found in the acupuncture arm, as

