compared with a 0.4 ± 1.2 units improvement in the sham-acupuncture arm.⁸ According to these data and ANOVA test with alpha of 0.05 and an 80% power, we calculated a minimal sample size of 66 patients (22 in each group) for the current study.

Randomization: Patients meeting inclusion/exclusion criteria were randomized to either SOC with acupuncture (true acupuncture), SOC with sham-procedure (sham-control) or SOC only (SOC-control) using 1:1:1 permuted block randomization. The permuted block randomization list was generated by Excel software. To guarantee allocation concealment, randomization was done by an independent research assistant who did not participate in any other parts of the research and assigned the group code to each participant according to the randomization list. The independent research assistant was blinded to the meaning of the group code.

Blinding: Data collectors, department physicians, physicians administering the sham-procedure and the statistician were blinded to the group allocation status; acupuncturist blinding is clearly not possible, however, contact time with patients was the same in both true acupuncture and sham-control arms (15-20 min). Patients receiving both true acupuncture and sham-procedure were told they are treated for their respiratory condition by acupuncture/acupressure. The group allocation status was revealed after completion of the study.

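### The primary dyspnea outcome spans 4 days with no named occasion or summary, and its single-occasion tests are not adjusted for the number of occasions

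*Combined protocol and SAP*

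**What the plan says.** All places are in the Combined protocol and SAP.

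- **Interventions** sets the schedule: "four daily consecutive treatment sessions and a 4-day follow-up".
- **Outcomes** defines the endpoint: "The primary outcome was dyspnea intensity pre- and post-treatment in the 4 days of follow-up". On timing: "It was measured daily, before and one hour after treatment" (in the SOC-control arm, the second reading follows the first evaluation). No reading, average or change score is singled out.
- **Minimal sample size** rests on an "ANOVA test with alpha of 0.05 and an 80% power", applied to an improvement in mBorg whose interval is not given.
- **Statistical analysis** provides ANOVA or Kruskal-Wallis by distribution and a 0.05 threshold. For multiplicity: "Bonferroni adjustment was used for multiple comparisons for each independent comparison of true acupuncture vs sham-control", with the other two pairs treated the same way. It describes no repeated-measures model, testing order over days or adjustment over occasions.
- The same section adds: "Since the variation of dyspnea intensity between day 1 and day 2 had a normal distribution, a multivariate linear regression analysis was performed", "in order to neutralize the effect of the different sociodemographic and medical covariates on the primary outcome in the 3 study arms". The result is Table 2, on the day 1 to day 2 change.
- **Results, Primary outcome** reports an omnibus p=0.014 after treatment on day 1 and states that significance lasted through day 3. The other days are in Fig. 2A, which is not shown.

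**The concern.** An outcome read twice a day for 4 days can be tested in many ways. Unless the text says which test carries the claim, a reader cannot tell which result is the single 5% test on which the trial was sized. Correcting for three arm pairs within an occasion does nothing about repeating the exercise on the next occasion.

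The regression does not fill the gap. The text links it to the primary outcome, but Outcomes does not define a day 1 to day 2 interval. The observed normal distribution is given as the reason for using regression; no reason is given for the interval. Table 2 takes SOC-control as reference, so it has no interval or p-value for acupuncture against sham (2.172 - 0.390 = 1.782 is available only as a point difference).

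Two things are at stake: the error rate attached to single-day p-values, and the absence of an effect estimate over the 4 days that define the outcome.

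**Working it through.** **Inputs from the documents.** Arms of 26, 24 and 22; Kruskal-Wallis for non-normal variables; threshold 0.05; day-1 omnibus p=0.014. Readings: 2 x 4 = 8, of which 4 are post-treatment.

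**Assumptions.** The correlation between occasions is not in the documents, so it is varied from 0 to 0.9 (exchangeable). Scores have mean 6 and SD 2, are rounded to 0.5 and bounded at 0 and 10. The table uses 60,000 null runs per setting.

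**1. The plan's own level.** One Kruskal-Wallis test at these arm sizes rejects in 4.8% of null runs (20,000 runs), so a single occasion holds its 5%. The stated 66 patients do not follow from the quoted effect and SDs, which give 5-8 per arm for an ANOVA; an effect size f=0.4, not stated in the documents, gives 22 per arm. That is a separate matter, and nothing below depends on it.

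**2. Four post-treatment occasions.** Under independence, 1 - 0.95^4 = 18.5%. Simulated (%):

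| Correlation | 0 | 0.3 | 0.5 | 0.7 | 0.8 | 0.9 |
|---|---|---|---|---|---|---|
| Any of 4 with p<0.05 | 17.9 | 17.1 | 15.5 | 13.3 | 12.0 | 9.8 |
| Smallest of 4 at or below 0.014 | 4.98 | 4.77 | 4.46 | 3.96 | 3.53 | 2.84 |
| Days 1, 2 and 3 all p<0.05 | 0.01 | 0.06 | 0.21 | 0.64 | 1.14 | 1.83 |

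Unrounded normal data gave 10.1-18.6% for the first row. An AR(1) correlation of 0.8 gave 15%.

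**3. Bonferroni over pairs does not carry over to occasions.** At least one Bonferroni-adjusted pair is significant in about 4% of null runs on one occasion and in 9-16% over 4 occasions.

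**4. The day-1 result adjusted over 4 occasions.**
- Bonferroni: 4 x 0.014 = 0.056.
- Holm: between 2 x 0.014 = 0.028 (days 2 and 3 small enough, day 4 above 0.05) and 4 x 0.014 = 0.056. The other days' p-values are not visible.
- Correlation-aware min-p (second table row): 0.028-0.048 at correlation 0.9-0.3, and about 0.050 at 0.

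**5. One overall test.** A baseline-adjusted ANCOVA of each patient's 4-day post-treatment mean rejects in 4.8-5.1% of null runs; its rank version in 4.9-5.1%.

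**The case against.** **The reported pattern is stronger than one lucky day.** This stands. Three successive significant days are rare under the null (last table row). The omnibus test plus acupuncture better than both controls on at least one of 4 occasions occurs in 0.2-0.4% of null runs with Bonferroni-adjusted pairs, or 0.9-1.5% with unadjusted pairs; the text does not say which kind its pairwise p-values are. The 10-17% belongs to an any-occasion rule that the documents do not state. But they state no other rule either, so neither pattern was the declared criterion.

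**The plan may have been fixed elsewhere.** Study design says "The study protocol was reviewed and approved by the Institutional Review Board (IRB"), and the trial was registered. The document under review also contains results. An earlier protocol may name an occasion, so the point is limited to the visible text.

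**A reader might also fault the lack of a primary arm pair.** That is not a defect: Bonferroni over all three pairs controls error within an occasion without ranking them, and the sized test is a three-arm ANOVA.

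**A reader might count 7 occasions** by adding the pre-treatment readings of days 2-4. The any-occasion rate would then be 12-27% at correlation 0.9-0.3. Whether those readings were tested depends on Fig. 2A, so this figure is conditional only.

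**The 4-day post-treatment mean is itself a choice.** This stands too. Outcomes mentions readings before and after treatment, and a within-session change is another possible reading. The fix must therefore justify its summary.

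**Conclusion.** The concern holds in limited form and should be fixed. The visible text names neither a primary occasion nor a 4-day summary, leaves occasions unadjusted, and reports no effect over the 4 days. If any significant post-treatment occasion counts, the false-positive chance is roughly two to three and a half times the nominal 5%. That size rests on 4 occasions and an assumed correlation of 0.3-0.9.

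A reader might infer that the dyspnea result is a false positive. The documents do not support that: the reported run of days is improbable under the null, and whether day 1 falls below 0.05 after adjustment depends on the method. A reader might also infer that the day 1 to day 2 interval was picked because it gave a favourable result. The text gives no reason for the interval, which is a gap in reporting and not evidence of selection.

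**What to change.** 1. Report one overall analysis over days 1-4: a repeated-measures model of post-treatment mBorg (second daily reading in SOC-control) with arm, occasion, arm-by-occasion and the day-1 pre-treatment score. Give the arm difference averaged over the 4 days, with the planned Bonferroni over the three pairs.
2. State why post-treatment readings are used. Show the pre-treatment readings of days 2-4, or the within-session change, as a supporting analysis.
3. Add a baseline-adjusted rank check, for example rank ANCOVA on each patient's mean post-treatment score. The scale is bounded, and the baseline medians in Table 1 are 8.0, 6.5 and 7.75.
4. Adjust the single-occasion tests by Holm or min-p over the number actually run, and state that number; or label them descriptive.
5. Give the reason for the day 1 to day 2 interval. Unless an earlier approved protocol prespecified them, label Table 2 exploratory and the overall analysis post hoc. A post hoc analysis cannot restore prespecified 5% control.

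**Cost.** The work is wording, one model, a supporting analysis and a rank check on data already collected. Some single-day p-values become less favourable, and a 4-day average dilutes an effect that fades by day 4. Power was compared with baseline adjustment on both sides, for an assumed effect of 0.5 SD against both controls. With the effect on days 1-3 only, at correlation 0.3/0.5/0.7/0.8, the 4-day mean had 56/57/71/83% power against 51/59/77/89% for at least one Bonferroni-adjusted occasion. It is thus similar or slightly weaker at correlation 0.5 or more. If the effect lasts all 4 days, the mean has more power: 82-98% against 60-92% for at least one Holm-adjusted occasion. The reason for the overall analysis is therefore that it gives one interpretable answer to the stated outcome, not that it always has more power.
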